"A Safety and Efficacy Study of a 1726nm Laser for the Treatment of Acne Vulgaris"

Cutera, Inc.

Protocol # C-20-PAC01

"A Safety and Efficacy Study of a 1726nm Laser for the Treatment of Acne Vulgaris"

1 PURPOSE

The purpose of this pivotal investigation is to evaluate the safety and efficacy of the investigational Cutera® 1726 nm laser system ([REDACTED] for the treatment of mild to severe acne vulgaris. Data from this investigation is intended to support a future 510(k) submission to obtain marketing clearance for the intended use listed above.

2 BACKGROUND INFORMATION

2.1 Acne Vulgaris

Acne Vulgaris is one of the most common dermatological conditions and affects a significant number of adolescents and adults.^{1, 2, 3} It develops in the pilosebaceous units of the skin from the following four factors—excess sebum production, the presence of the *Propionibacterium acnes* (*P. acnes*) bacteria, follicular epidermal hyper proliferation that plugs the follicle, and inflammation. It can have severe psychological effects and can leave the patient with severe skin scarring.^{3, 4, 5, 6}

Currently, standard acne treatment includes the use of topical and systemic medications, with the choice of treatment often determined by disease severity, but also by patient preferences and cost considerations.⁵

Topical treatments work to reduce the level of follicle obstruction and reduce the bacterial load and inflammation. Of the topical medications, retinoids, benzoyl peroxide, azelaic acid, salicylic acid, and antibiotic solutions are used regularly, either alone or in combination with other treatments. Combinations have been reported to increase effectiveness, especially with benzoyl peroxide or retinoids and topical antibiotics such as clindamycin, erythromycin, or tetracycline. Topical retinoids are indicated as a first-line treatment in patients with non-inflammatory lesions.⁶ Because the use of topical antibiotics may lead to resistance in the *P. acnes* bacteria, the use of benzoyl peroxide, retinoids, and other non-antibiotic medications are an important adjunct to antibiotic therapy.^{3, 6}

Systemic medications include oral antibiotics, anti-androgens, and isotretinoin. Oral antibiotics, among other potential mechanisms of action, target bacteria and directly reduce inflammation. Oral anti-androgens such as low estrogen oral contraceptives, are indicated after failure of standard antibiotic regimens, and act to reduce the sebum driving effects of testosterone.⁵ Oral isotretinoin has remained the most effective systemic medication for moderate to severe acne as well as for refractory cases. It acts to affect cell progression, differentiation, survival, and apoptosis, as well as reduces sebum production, comedogenesis, *P. acnes* load, and inflammation.^{5, 6, 7}

Each of these treatments has its limitations. For example, oral isotretinoin has serious side effects of teratogenicity and possibly psychiatric effects, which can limit the safety and utility of the drug for many patients.⁷ Although topical and oral antibiotics have been used successfully in the treatment of acne for decades, the concern over antibiotic resistance continues to grow.³ As such, alternative, yet effective new treatments are still needed. While topical and systemic medications remain the gold standard for treatment of acne vulgaris, laser therapy which has emerged in recent decades as an effective treatment of acne vulgaris may be an additional option for some patients, especially for those who cannot tolerate standard treatments or for refractory cases.⁶

There are two main mechanisms of action for treatment of acne with light therapy. First, blue or red light sources, green or yellow light lasers, and intense pulsed light (IPL) devices kill *P. acnes* directly. Second,

radiofrequency (RF) devices and near infrared light lasers damage sebaceous glands.⁶ Blue and red LED light sources have resulted in variable, but successful treatment of inflammatory acne.^{8, 9} Mid-infrared devices, in the ranges of 1320 and 1450 nm lasers (which mainly target water and to a much lesser extent sebum), have shown efficacy in treating acne, but also may result in pain for the patient, which is a limitation to some of these treatments.^{10, 11, 12} Photodynamic therapy (PDT) using red light at higher doses and longer incubation periods (≥ 3 hours) can directly inhibit sebaceous gland function through destroying sebocytes, but it is also associated with undesirable side effects such as intense pain during irradiation, long-lasting erythema, and oozing and crusting from epidermal damage.^{6, 13, 14, 15}

Although the wavelengths above improve acne, none are preferentially absorbed directly by the sebaceous glands.¹⁶ Exogenous chromophores introduced into the sebaceous gland complex (such as topically delivered light absorbing gold microparticles) help aid in sebaceous gland selective photothermolysis with infrared light, and the treatment is well-tolerated.^{15, 16} Microparticles are currently indicated for use as an accessory to 1064 nm lasers to facilitate this photothermal heating of sebaceous glands for the treatment of mild to moderate inflammatory acne vulgaris [K181518].

[REDACTED]

Cutera, Inc.

Protocol # C-20-PAC01

"A Safety and Efficacy Study of a 1726nm Laser for the Treatment of Acne Vulgaris"

[REDACTED]

[REDACTED]

[REDACTED]

[REDACTED]

3 STUDY OBJECTIVE

The primary objective is to evaluate the safety and efficacy of the investigational Cutera® 1726 nm laser system [REDACTED] for the treatment of mild to severe acne vulgaris. Data from this investigation is intended to support a future 510(k) submission to obtain marketing clearance for the intended use listed above.

4 STUDY DESIGN

This is a multi-center, prospective, open-label, single-arm study. Up to 15 study sites will enroll and initiate treatment on up to 107 male and female subjects, ages 16 to 60 years, who present with mild, moderate or severe facial acne at baseline, pass all eligibility criteria and desire laser treatment for their acne. Enrolled subjects will receive [REDACTED] laser treatments on the face [REDACTED]. Subjects will be followed at approximately 10 [REDACTED] days post each treatment (via phone) and at 4 [REDACTED], 12 [REDACTED] and 52 [REDACTED] weeks post-final treatment.

Subjects will be required to undergo a 1 month (30 day) washout period from topical retinoids and other systemic or topical acne medications prior to baseline, and for the duration of the study. If the acne medication is topical, the washout applies to use on the face only. [REDACTED]
[REDACTED]

4.1 Study Duration

Subjects enrolled in this study will be asked to participate for up to approximately 18 months [REDACTED]

4.2 Study Outcome Measures - Effectiveness

4.2.1 Primary Endpoint

The primary outcome measure to evaluate the efficacy of the investigational Cutera® 1726 nm laser system for the treatment of mild to severe acne vulgaris is the percent reduction in inflammatory acne lesion count across the entire face (excluding areas not treated) for each subject from baseline to 12 weeks [REDACTED]

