5.1.1 Inclusion Criteria

To be included in the study, subjects must meet all of the following Inclusion Criteria:

1.	Female or Male, 16 to 60 years of age (inclusive).
2.	████████ Fitzpatrick Skin Type I-IV ¹⁹ ; ██████████ Fitzpatrick Skin Type V-VI ¹⁹
3.	Has clinically diagnosed acne vulgaris of severity grade 2 – 4 on the face ██████████ using the Investigator's Global Assessment Scale ██████████
4.	Has ██████████ inflammatory acne lesions on the face as determined by the Investigator (or qualified designee).
5.	Subject (and parent or legal guardian if subject is a minor under age 18) must be able to read, speak, and understand English and sign the Informed Consent Form.
6.	Willing to stop using topical retinoids and other acne medications for 1 month (30 days) prior to baseline and for the duration of the study. If the acne medication is topical, the washout applies to use on the face only.
7.	Willing and able to adhere to the treatment and follow-up schedule and pre/post-treatment care instructions.
8.	Willing to have very limited sun exposure (including avoiding tanning booths, sun lamps, sunbathing) and use an approved sunscreen of SPF 30 or higher on the face every day for the duration of the study, including the follow-up period.
9.	Willing to have photographs taken of the face and agree to the use of photographs for presentation, educational or marketing purposes.
10.	Agree to not undergo any other procedure(s) or add any new treatment modalities in the target area during the study.

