11.3 Primary Effectiveness Endpoint – Percent Change from Baseline in Inflammatory Lesion Counts

Percent Change from Baseline in Inflammatory Lesion Counts (ILC) is calculated as:

$$\frac{100 \times (\text{Follow-Up Visit ILC} - \text{Baseline ILC})}{\text{Baseline ILC}}$$

such that a negative result reflects a decrease in the inflammatory lesion counts, while a positive result reflects an increase. A decrease in the inflammatory lesion counts indicates improvement, therefore negative values reflect improvement.

[REDACTED]

[REDACTED]
[REDACTED]

[REDACTED]
[REDACTED]

[REDACTED]

[REDACTED]
[REDACTED]

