11.10 Statistical Methods

Categorical data will be summarized using frequency tables, presenting the subject counts and relative percentages. McNemar's chi-square may be used to assess within-subject changes in a bivariate response variable.

Continuous variables will be summarized by the mean, standard deviation, median, minimum and maximum. Within-subject changes (Change-from-Baseline) will be analyzed parametrically using the

Paired t-test if the differences are normally distributed, or non-parametrically using the Sign-Rank Test if the differences are not normally distributed. Mid study evaluation of data may be performed to facilitate clinical study report writing. Investigators and panelists will remain blinded to such evaluation.

Appropriate statistical software will be used to perform all analyses. Exact confidence intervals will be generated for estimates of proportions. Asymptotic confidence intervals will be generated for estimates of means. Except where otherwise noted, the p-values of all tests will be reported without any correction for the multiplicity of tests performed.

The figure consists of a series of 10 horizontal bars, each composed of two black bars. The top bar in each pair is significantly thicker than the bottom one. The bars are arranged vertically. The second bar from the top has a small, irregular white rectangular gap in its center, while the other bars are solid black. The bars are set against a white background.

Confidential and Proprietary

Page 30 of 48

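### Does leaving untreated facial areas out of the primary endpoint inflate the percent reduction?

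*Combined protocol and SAP*

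**What the plan says.** Section 4.2.1 gives the primary outcome as the "percent reduction in inflammatory acne lesion count across the entire face (excluding areas not treated) for each subject from baseline to 12 weeks"; the sentence then runs into a redaction. Section 11.3, headed as the same primary endpoint, opens its formula with "Percent Change from Baseline in Inflammatory Lesion Counts (ILC) is calculated as". The formula is 100 × (follow-up ILC − baseline ILC) / baseline ILC, "such that a negative result reflects a decrease in the inflammatory lesion counts, while a positive result reflects an increase". Several redacted lines follow it.

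Inclusion criterion 4 in section 5.1.1 requires a number, blacked out, of "inflammatory acne lesions on the face as determined by the Investigator (or qualified designee"). Section 4 states "This is a multi-center, prospective, open-label, single-arm study" and says that subjects receive "laser treatments on the face", with the number and schedule redacted. Section 11.10 compares within-subject changes by "Paired t-test if the differences are normally distributed, or non-parametrically using the Sign-Rank Test if the differences are not normally distributed".

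**The concern.** The excluded region is described by whether it was treated. It is not listed as named anatomical sites. Treatment follows baseline, there is more than one session, and the trial is open-label with no control arm to share a counting bias. One can therefore picture areas being skipped at a later session because of discomfort or a reaction, and so leaving the endpoint.

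The formula in section 11.3 also does not repeat the exclusion, and criterion 4 counts the face without it. If the baseline count covered the whole face and the week-12 count covered treated areas only, every baseline lesion in untreated skin would be scored as cleared. The device would then show a reduction with no effect at all, in a study meant to support marketing clearance.

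**Working it through.** **Figures in the plan.** The only design figure visible is the ceiling in section 4, "Up to 15 study sites will enroll and initiate treatment on up to 107 male and female subjects". It is not in dispute and has no bearing on the counted region. No effect size, standard deviation, alpha or power is visible, so there is no stated result to reproduce. The check is a reading of the text, followed by arithmetic on assumed values.

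**Reading the sections together.**

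1. In section 4.2.1 the exclusion is attached to the lesion count, and the change in that count is taken from baseline to week 12. On plain grammar it applies at both ends.
2. Section 11.3 carries the primary-endpoint heading and uses the single term ILC for both visits. A formula need not restate a region that the endpoint definition has already given.
3. Criterion 4 is an entry requirement. Nothing visible says that the eligibility count is the baseline ILC, so it is no evidence of a whole-face denominator.
4. No visible sentence says that the region is settled after baseline, that operators set it, or that areas may be dropped for intolerance or a reaction. Facial areas that the protocol never treats are an equally natural reading. Under that reading the region is known before the baseline count, and selection after baseline cannot occur.

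**Arithmetic.** Let f be the share of baseline lesions in untreated areas, and let r and s be the proportional reductions in treated and untreated areas. All three are assumed; the documents give none of them. The percent change on the section 11.3 scale is:

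- whole face at both visits: −100 × [(1 − f)r + fs]
- treated area at both visits: −100 × r
- whole-face baseline, treated-area follow-up: −100 × [1 − (1 − f)(1 − r)]
- treated-area baseline, whole-face follow-up: 100 × {[(1 − f)(1 − r) + f(1 − s)]/(1 − f) − 1}

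| Assumed truth | f | Whole / whole | Treated / treated | Whole / treated | Treated / whole |
|---|---|---|---|---|---|
| r = 0, s = 0 | 5% | 0.0 | 0.0 | −5.0 | +5.3 |
| r = 0, s = 0 | 10% | 0.0 | 0.0 | −10.0 | +11.1 |
| r = 0, s = 0 | 20% | 0.0 | 0.0 | −20.0 | +25.0 |
| r = 50%, s = 0 | 5% | −47.5 | −50.0 | −52.5 | −44.7 |
| r = 50%, s = 0 | 10% | −45.0 | −50.0 | −55.0 | −38.9 |
| r = 50%, s = 0 | 20% | −40.0 | −50.0 | −60.0 | −25.0 |
| r = 50%, s = 50% | 20% | −50.0 | −50.0 | −60.0 | −37.5 |
| r = 30%, s = 50% | 20% | −34.0 | −30.0 | −44.0 | −17.5 |

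Example for f = 20%, r = 50%, s = 0: the whole-face change is −100 × (0.8 × 0.5) = −40.0, and the whole/treated pairing gives −100 × (1 − 0.8 × 0.5) = −60.0.

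The matched treated-area column is 0 when there is no effect. It equals the whole-face result when the response is uniform, and it is the smaller reduction when untreated skin improves more (−30.0 against −34.0). The two mismatched columns err in opposite directions, and neither pairing is described in the plan.

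**Choice of region.** A Poisson simulation with no true effect, 30 lesions spread over 5 or 6 regions and one region dropped from both visits gave these pooled changes:

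- region dropped at random: about 0%
- region with the worst change dropped after follow-up was seen: about −15% to −16%
- region with the lowest baseline count dropped: about −9% to −10%
- region with the highest baseline count dropped: about +14%

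Bias with a common region therefore requires that the region be picked by its counts. Nothing in the documents describes that.

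**The case for a change.** The strongest opposing argument is that the exclusion refers to treatment delivered, which is complete only after the sessions that follow baseline. The visible text does not say who fixes the region, when, or whether it can change between sessions, and it does not expressly say that the same region is used at both visits. The one visible statement on blinding, in section 11.10, covers the mid-study look at the data and not the counting of lesions. With no control arm, a region chosen by outcome could produce about 15% to 16% reduction from nothing, even when it is applied equally to both visits.

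The gap in the visible text is real, and the arithmetic is right. The gap does not show a fault in the plan. Section 4.2.1 breaks off in a redaction just where such a rule would come, redacted lines follow the formula in 11.3, and sections 4.4 and 6 are absent from the public copy. What is withheld cannot be counted as omitted. Nor can it be said that the staff who treat also count: section 11.10 shows that panelists exist, and the visible text does not give their role.

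A whole-face result would be informative, and keeping later-skipped areas in the count is a defensible choice. Both answer a different question from the one the plan openly states.

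**Conclusion.** The concern does not hold. It needs either a region chosen by operators after baseline or one formula in which ILC means two different regions, and the visible text states neither. The spurious reductions of 5% to 20% with no effect, and the 52.5% to 60% figures, all come from that second, unsupported pairing. Read as written, with one region at both visits, the exclusion produces no mechanical bias provided the region is not selected on its counts.

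The remaining difference, 50% for treated skin against 40% to 47.5% for the whole face, lies between two estimands and is not an error of calculation. It rests on assumed values: 5% to 20% of lesions in untreated areas, no change there, and a 50% reduction elsewhere. It reverses if untreated skin improves more. This conclusion depends on reading the exclusion as applying to both visits and on treating the withheld text as part of the plan.

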4.3 Study Outcome Measures - Safety

Overall safety of the Cutera® 1726 nm laser system for the treatment of mild to severe acne vulgaris will be assessed by a review of the totality of all reported adverse events.

The figure displays a 6x6 grid of black and white bars, representing a 2D convolutional feature map. The bars are arranged in a repeating pattern of vertical and horizontal segments. The heights and widths of the bars vary, indicating the magnitude of feature activation across the spatial dimensions. The grid is composed of 36 individual bars, with the first bar in the top-left corner being black and the last bar in the bottom-right corner being white.

4.5 Safety Assessments

4.5.1 Incidence and Severity of Adverse Events

Following the first treatment, adverse events (AEs)/ adverse device effects (ADEs) will be assessed post-treatment and at each subsequent subject visit [REDACTED]

Confidential and Proprietary

Page 13 of 48

16 APR 2021

4.6 Photographs

Standardized digital photographs will be taken of each subject's face at baseline, prior to all laser treatments and at each follow-up visit, according to the following procedures:

- Subject will have recently cleansed skin;
- Subject's hair will be pulled away from his or her face;
- Subject will remove jewelry;
- A black drape will be placed around the subject's shoulders;
- A neutral facial posture will be maintained;

4.7 Study Discontinuation

The Investigator and/or the Sponsor has the right to terminate this study at any time. Reasons for terminating the study may include, but are not limited to, the following: incidence or severity of adverse events in this or other studies indicates a potential health hazard to subjects; subject enrollment is unsatisfactory; number of protocol deviations is unacceptable; data recording is inaccurate or incomplete; or questionable study site compliance with Good Clinical Practice, FDA 21 CFR Part 812 and other applicable regulations.

4.8 Investigator Selection

The Investigator(s) will be invited to participate in the study based on medical specialty, experience diagnosing and treating acne vulgaris, experience conducting clinical research studies and/or experience in the use of laser based devices for aesthetic indications and/or dermatology applications. Access to potential study subjects and the Investigator's sincere interest in this study along with expressed willingness to cooperate with the study process and requirements will also be considered.

5 STUDY POPULATION

5.1 Subject Recruitment and Selection

Male or female subjects, ages 16 to 60, with Fitzpatrick Skin Type I-VI¹⁹ who present with mild, moderate, or severe facial acne vulgaris at baseline (and desire laser treatment for facial acne) will be included. Subjects will be recruited to participate from the local population. Subjects may also be recruited from the Investigator's or study site's existing patient database or from patients who present themselves to the study site requesting treatment. Only subjects who meet all eligibility criteria and who provide written informed consent/assent will be enrolled into the study.

Each subject will be evaluated to assess his/her suitability for entry into the study according to the following inclusion and exclusion criteria.

5.1.1 Inclusion Criteria

To be included in the study, subjects must meet all of the following Inclusion Criteria:

1.	Female or Male, 16 to 60 years of age (inclusive).
2.	████████ Fitzpatrick Skin Type I-IV ¹⁹ ; ██████████ Fitzpatrick Skin Type V-VI ¹⁹
3.	Has clinically diagnosed acne vulgaris of severity grade 2 – 4 on the face ██████████ using the Investigator's Global Assessment Scale ██████████
4.	Has ██████████ inflammatory acne lesions on the face as determined by the Investigator (or qualified designee).
5.	Subject (and parent or legal guardian if subject is a minor under age 18) must be able to read, speak, and understand English and sign the Informed Consent Form.
6.	Willing to stop using topical retinoids and other acne medications for 1 month (30 days) prior to baseline and for the duration of the study. If the acne medication is topical, the washout applies to use on the face only.
7.	Willing and able to adhere to the treatment and follow-up schedule and pre/post-treatment care instructions.
8.	Willing to have very limited sun exposure (including avoiding tanning booths, sun lamps, sunbathing) and use an approved sunscreen of SPF 30 or higher on the face every day for the duration of the study, including the follow-up period.
9.	Willing to have photographs taken of the face and agree to the use of photographs for presentation, educational or marketing purposes.
10.	Agree to not undergo any other procedure(s) or add any new treatment modalities in the target area during the study.

5.1.2 Exclusion Criteria

Subjects will be excluded from the study if they meet any of the following Exclusion Criteria:

1.	Has clinically diagnosed acne vulgaris of severity grade 0 or 1 on the face [REDACTED] using the Investigator's Global Assessment Scale.
2.	Prior treatment to the target area during participation in a clinical trial of another device or drug within 1 month (30 days) prior to study participation.
3.	Prior treatment to the target area within 3 months of study participation including chemical peel, dermabrasion, microneedling, radiofrequency treatment, laser or light-based procedures, cryodestruction or chemodestruction, intralesional steroids, photodynamic therapy, or acne surgery.
4.	Prior injection of botulinum toxin in the target area within 3 months of study participation and for the duration of the study.
5.	Prior injection of collagen, hyaluronic acid filler or other dermal filler in the target area within 6 weeks of study participation.
6.	Systemic use of retinoid, such as isotretinoin, within 6 months of study participation.
7.	History of malignant tumors in the target area.
8.	Excessive facial hair (e.g. beards, sideburns, moustaches, etc.) that would interfere with diagnosis or assessment of acne vulgaris in the target area (okay if shaved).
9.	Pregnant and/or breastfeeding or planning to become pregnant during the study.
10.	Presence of any skin condition in the target area (e.g. eczema, psoriasis, dermatitis, rash, papulo-pustular rosacea, infection) that would interfere with the diagnosis or assessment of acne vulgaris.
11.	Any medical condition that, in the opinion of the Investigator, would interfere with patient's participation in the full study protocol (e.g. severe Diabetes Mellitus or Cardiovascular Disease).
12.	Suffering from diagnosed coagulation disorders or taking prescription anticoagulation medications.
13.	History of diagnosed immunosuppression/immune deficiency disorders or currently using immunosuppressive medications.
14.	History of diagnosed connective tissue disease, such as systemic lupus erythematosus or scleroderma.
15.	Any use of medication that is known to increase sensitivity to light according to Investigator's discretion.
16.	History of disease stimulated by heat, such as recurrent herpes simplex and/or herpes zoster (shingles) in the target area, unless treatment is conducted following a prophylactic regimen.
17.	History of radiation to the target area, currently undergoing treatment for skin cancer in the target area, or undergoing systemic chemotherapy for the treatment of cancer.
18.	History of diagnosed pigmentary disorders (including vitiligo) in the target area.

19.	Excessively tanned on the face or unable/unlikely to refrain from tanning on the face during the study.
20.	As per the Investigator's discretion, any physical or mental condition which might make it unsafe for the subject to participate in this study.

[figure not shown]
